#### **9.4.1 Exposures**

Not Applicable

#### **9.4.2 Outcomes**

See sections 9.4.3 & 9.4.4

#### **9.4.3 Primary Outcomes**

The main objective of this IPF registry is to gain further knowledge on the characteristics, management, progression and outcomes of patients with IPF as treated under real-world, clinical practice conditions in Greece.

More specifically, this registry is going to:

- Provide a comprehensive clinical picture for IPF
- Track access to health care and cost of caring for IPF patients over time
- Examine the implementation of treatment guidelines [2], used on patients diagnosed with IPF, according to the existing diagnosis guidelines [1]
- Characterization of patients on different treatments

For more detailed information, please refer to [Annex 3](#).

#### **9.4.4 Secondary Outcomes**

This registry documents management and treatment of IPF-patients in real-world clinical practice. One objective of this registry is to document drugs used for IPF.

The following drugs will be documented in detail in terms of drug name, dosage, start and stop dates, including combinations of the mentioned drugs:

- Steroids
- Immunomodulators (azathioprine, cyclophosphamide, cyclosporine A, mycophenolate mofetil etc)
- N-Acetylcysteine
- Pirfenidone
- Nintedanib
- Anticoagulants

- Vit-K antagonist
- Heparin
- Antiplatlet therapy (if yes it will be specified if high dose antiplatlet therapy)
- Aspirin (if yes it will be specified if used as antiplatelet)
- GERD medication
- PDE-5 inhibitor (sildenafil, tadalafil)
- Endothelin receptor antagonist (bosentan, ambrisentan, macitentan)
- Long term oxygen therapy
- Listed for lung transplantation
- NSAIDs, other than aspirin
- Hormone replacement therapy
- Hormonal contraceptives
- Anti-VEGF drugs
- NOAC
- Other (specify)

#### **9.4.5 Covariates**

Due to the non - interventional nature and design of the observational study, this registry does not require diagnostic/therapeutic procedures or strict timeline visit schedule. Patients will receive treatment according to standard clinical practice with regards to visit frequencies, type of performed assessments and according to local prescription requirements.

Following identification of a potential patient, the investigator will follow the below listed procedures:

1. Review of individual patient's medical history, to confirm that the inclusion/exclusion criteria are met.
2. Explanation of the study objectives to the patient and receipt of signed and dated informed consent, after providing the patient with sufficient time to read carefully and understand the information sheet.
3. Data collection from the medical records of eligible for enrollment patients, as required by eCRF, and eCRF completion.

Please refer to [Section 11.2](#) for details regarding Adverse Event and Serious Adverse Event Collection and Reporting.

A tabulated schedule of assessments that provide information regarding the recommended timeline of data collection and represents the standard clinical care of IPF treated patients is listed below in [Table 1](#). The exact definitions of the variables can be found in Appendixes 2-5.

Table 1. List of variables to be documented (if available) at scheduled visits

Variable (Please refer to Annex 4 )	Assessment	Follow up**
Eligibility criteria	x	
Baseline information (assessment)		
(Socio-)demographic variables: age, gender, race, height, index employment status, insurance status	x	
Weight, blood pressure, heart rate	x	x
(Possible) IPF risk factors		
Cigarette smoking incl. pack years (Categorized as never/past/current/unknown. For past/current, specify packs/year and for past, number of years smoking one pack per day); environmental and occupational exposure; alcohol and substance abuse; exposure to drugs associated with IPF ; exposure to viral infection possibly related to IPF; gastro-oesophageal reflux; genetic factors (family history); others	x	
Co-morbidities (Please refer to Annex 5 )	x	x
IPF		
Baseline information (assessment) on IPF		
First symptoms; date of first diagnosis, dates and results of HRCT, surgical lung biopsy, bronchoalveolar lavage.	x	
Symptoms		
9.4.5.1 Dyspnea, cough fatigue, dizziness, chest pain, anxiety [20]	x	x
Functional assessment		
Lung function test (VCin, FVC, FEV1, TLC; DLCO; pO2, pCO2) [21]		
6-minute walk distance	x	x
Cardiopulmonary exercise testing (CPET;)		
Serologic evaluation– Autoimmune Biomarkers (laboratory values)		
Rheumatoid factor, anti-cyclic citrullinated peptide, and anti-nuclear antibody titer and pattern*	x	
Others e.g. SCL-70, SS-A, SS-B		x

Proprietary confidential information © 2018 Boehringer Ingelheim International GmbH or one or more of its affiliated companies

BNP/NT-pro BNP		
Hb, AST, ALT, total bilirubin		
Pharmacological treatment( start date, stop date and daily dose)		
Past/discontinued: drugs (e.g. steroids yes/no/unknown). Detailed list of drugs in Annex 4	x	x
Current: drugs by class and/or name	x	x
Participation in IPF trial	x	x
Non-pharmacological treatment	x	x
Long-Term-Oxygen-Therapy (liquid and/or concentrate)	x	x
Lung transplantation score and assessment if the patient is currently listed for participation in lung transplantation	x	x
Physician assessment		
Physician's clinical rating of the probable course of IPF (stable, slow or rapid progression), based on available FVC results, DLCO results, physical examination, hospitalizations/events between the visits	*** x	x
Management of IPF and physician contacts		
Number of physician visits (own office, other physicians)	*** x	x
Number and type of IPF related procedures	*** x	x
Outcomes of Interest (please refer to Annex 3)		
	*** x (except for mortality, hospitalization, please see below)	x
Clinical events and hospitalizations		
specifically due to: (acute) worsening of respiratory function including pneumonia; IPF-exacerbations; manifest pulmonary or cardiovascular complications; pulmonary rehabilitation; pulmonary embolism; pneumothorax; cardiac failure (please refer to Annex 3 for detailed description of the outcomes of interest).	*** x	x
Number of days in hospital or in rehabilitation; work days lost due to IPF	*** x	x
Physical examination and vital signs		
Risk of bleeding and thrombosis	x	x

Survival status (vital status)(please refer to Annex 3)		x
--	--	---

For abbreviations, please refer to glossary.

\* As recommended in the ATS/ERS guidelines for distinguishing connective tissue disease from IPF

\*\*3-months (+/- 1 month), 6-months (+/- 1 month), 12-months (+/- 2 month), 18-months (+/- 2 month) and 24 months (+/- 2 months)

\*\*\* *the past 12 months*

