## **8. RESEARCH QUESTION AND OBJECTIVES**

The overall objective of the present IPF Registry is to gain further insight on the characteristics, management, disease progression and the outcomes of patients with IPF, as diagnosed and treated under real-world, clinical practice conditions in Greece.

More specifically, this registry will be used to:

- Provide a comprehensive clinical picture of IPF
- Track access to health care and cost of caring for IPF patients over time
- Examine the implementation of treatment guidelines [2], used on patients diagnosed with IPF, according to the existing diagnosis guidelines [1]
- Characterization of patients on different treatments

Furthermore, this project aims to provide information regarding survival and mortality causes, IPF exacerbations as well as IPF patient co-morbidities including myocardial infarction, CNS infarction, other arterial thromboembolic events, deep vein thrombosis, hemorrhage, gastrointestinal perforation and pulmonary hypertension (please refer to [Annex 3](#)). In addition, data regarding IPF patient hospitalization will be collected and evaluated with regards to potential respiratory causes, and there will be documentation of treatment patterns and economic aspects. Patients will be followed up for 2 years and information regarding IPF treatment changes since the last visit will be collected.

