## **9.4       VARIABLES**

At baseline, a relevant patient history will be recorded including IPF-related events up to 12 months prior to this visit. The variables to be recorded are listed below as well as in [Annex 4](#):

- Basic (socio-)demographic data including age, gender and race
- Vital Status
- Physical and vital signs examination
- Cardiopulmonary exercise testing (6-minute walk distance and CPET, if performed)
- IPF risk factors (e.g cigarette smoking including pack years, alcohol and substance abuse, environmental and occupational exposure, exposure to drugs associated with IPF, exposure to viral infection possibly related to IPF, gastro-esophageal reflux, genetic factors - family history)
- Co-morbidities.
- Risk of bleeding and thrombosis
- Collection of pre-specified outcome data, only for newly diagnosed patients (such as acute respiratory worsening, exacerbations, hospitalization due to any cause and due to IPF). Please, refer to [Annex 3](#)
- Recording of therapeutic regimens. Assessment of the intensity of treatment, frequencies and resource utilization for pharmaco-economic analyses.
- Methods and procedures used in the diagnosis of IPF and date of diagnosis (HRCT: UIP pattern, possible, inconsistent UIP pattern and not available and SLB: UIP pattern, probable, possible or inconsistent UIP pattern)
- IPF symptoms: Dyspnea, cough, weight loss, fatigue, dizziness, chest pain, anxiety, clubbing, bibasilar crackles
- Autoimmune Biomarker results (No additional specimen will be collected. Only already existing data will be used from exams that have been performed according to the routine clinical practice of the physicians),
- Assessment of function (including lung function, cardiopulmonary exercise testing and/or exercise capacity if available, laboratory values)
- IPF treatment modalities (detailed information on prescribed drugs and dose; previous treatment; start and end dates of previous treatments; non-pharmacological treatment; listing and score for lung transplantation). For the treatments that detailed information will be requested, please refer to [Annex 4](#)

Proprietary confidential information © 2018 Boehringer Ingelheim International GmbH or one or more of its affiliated companies

- Physician's clinical rating of the probable course of IPF (stable, slow or rapid progression)

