## **6.7 BASELINE, TIME WINDOWS AND CALCULATED VISITS**

No visit windows will be used. The CRF nominal visits will be applied for the analysis. Unscheduled visits are not expected and if any they will not be counted for primary and secondary endpoints. However, they will be considered for the safety analysis regarding Adverse Events (if any).

The baseline value will be the first measurement made after the enrolment to the study.

Baseline information will be presented appropriately in the “by visit” summaries.

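### Undated health-care-use counts cover 12 months at baseline but an unstated period at follow-up, and the visible SAP gives no time denominator, so by-visit tables of raw counts could show a false trend

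*Protocol*

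**What the plan says.** **Objective.** Protocol section 8 sets out to "Track access to health care and cost of caring for IPF patients over time". Section 9.4.3 and SAP 5.1 repeat it, and SAP 5.1 lists the description of resource use among the primary endpoints. Protocol section 7.6 expects most health-economic items to be priced later.

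**Baseline look-back.** Protocol section 9.4 says that at baseline "a relevant patient history will be recorded including IPF-related events up to 12 months prior to this visit". In Table 1 (section 9.4.5) the rows "Number of physician visits (own office, other physicians"), number and type of IPF procedures, and "Number of days in hospital or in rehabilitation; work days lost due to IPF" carry a triple asterisk in the baseline column only. The footnote explains it as "the past 12 months".

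**Follow-up look-back.** The same rows have a plain cross at follow-up. The schedule is "3-months (+/- 1 month), 6-months (+/- 1 month), 12-months (+/- 2 month), 18-months (+/- 2 month) and 24 months (+/- 2 months"). No look-back is attached to these rows, and Annex 4 has no entry for numbers of physician visits, procedure counts, rehabilitation days or lost work days. The nearest wording is "hospitalizations/events between the visits", which belongs to the physician-rating row. Section 8 speaks of the time from one visit to the next, but only for changes of treatment.

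**Analysis.** SAP 6.7 states: "No visit windows will be used. The CRF nominal visits will be applied for the analysis". It also places baseline in the by-visit summaries. SAP 7 summarises continuous variables by mean, SD, median, minimum and maximum. SAP 7.4 adds only that primary endpoints are described overall and by time since diagnosis.

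**The concern.** A count means something only together with the time it covers. Here one row of Table 1 covers 12 months in its first column and, on the natural reading, 3 or 6 months in the later ones. If the general SAP rules are applied to that row as they stand, the visit means differ because the periods differ, whether or not use of care has changed.

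The likely misreading is that contacts and lost work days drop sharply once patients enter the registry and then climb again. Costs built on the raw counts would carry the same pattern. Since the objective is a description over time, the absence of hypothesis tests gives no protection: the description itself would be wrong.

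**Working it through.** The documents give no figure for health-care use, so there is nothing to reproduce.

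**Inputs**
- Baseline look-back: 12 months (Table 1 footnote; section 9.4).
- Follow-up visits: months 3, 6, 12, 18 and 24, with tolerances of 1, 1, 2, 2 and 2 months (section 9.3.3; Table 1 footnote).
- Assumption A: follow-up counts cover the time since the previous visit.
- Assumption B: use is constant. The documents give no rate, so 3, 6 and 12 contacts per year are shown. The ratios do not depend on the rate.

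**Step 1: expected count under constant use.** Expected count = yearly rate × months covered / 12.

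| | Baseline | M3 | M6 | M12 | M18 | M24 |
|---|---|---|---|---|---|---|
| Months covered | 12 | 3 | 3 | 6 | 6 | 6 |
| 3 per year | 3 | 0.75 | 0.75 | 1.5 | 1.5 | 1.5 |
| 6 per year | 6 | 1.5 | 1.5 | 3 | 3 | 3 |
| 12 per year | 12 | 3 | 3 | 6 | 6 | 6 |

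Baseline to month 3: 1 − 3/12 = 75% fall. Month 6 to month 12: 6/3 = 2, a doubling. Month 12 against baseline: 6/12 = 50%, so the rebound is only partial.

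**Step 2: spread within one nominal visit.** The visit ranges are 2–4, 5–7, 10–14, 16–20 and 22–26 months. Shortest gap = earliest date of this visit − latest date of the previous one; longest gap = latest − earliest.

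| Visit | Shortest | Longest | Ratio |
|---|---|---|---|
| M3 | 2 | 4 | 2 |
| M6 | 5 − 4 = 1 | 7 − 2 = 5 | 5 |
| M12 | 10 − 7 = 3 | 14 − 5 = 9 | 3 |
| M18 | 16 − 14 = 2 | 20 − 10 = 10 | 5 |
| M24 | 22 − 20 = 2 | 26 − 16 = 10 | 5 |

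These are extremes: they need two consecutive visits at opposite ends of their tolerances.

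**Step 3: missed visits and early leavers.** Missing month 3 makes month 6 cover 6 months instead of 3 (doubled). Missing month 6 makes month 12 cover 9 instead of 6 (1.5-fold). Missing month 12 makes month 18 cover 12 instead of 6 (doubled). Section 9.5 also files the last assessment of an early leaver under the next planned visit, so a short period can sit under a later visit label.

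**Step 4: common scale.** Dividing each entry in Step 1 by the months covered gives the same value at all six points, and the pattern disappears. Yearly sums do the same at nominal times: 3 + 3 + 6 = 12 and 6 + 6 = 12 months, each comparable with baseline. Within the tolerances the first sum covers 10–14 months and the second 22 − 14 = 8 to 26 − 10 = 16, so yearly totals are approximate unless actual dates are used.

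**Step 5: if Assumption A is wrong.** A 12-month look-back at every follow-up visit would remove the fall. But it would collect 5 × 12 = 60 months of recall over the 33 calendar months from month −9 to month 24, so use would be counted more than once. Either way the look-back has to be stated before the counts can be interpreted.

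**The case against.** A reader might infer that the planned tables will show a fall and rebound in all resource use. The documents do not support that, for these reasons.

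- **The follow-up look-back is not stated.** Time since the previous visit is the natural reading, but the wording that suggests it belongs to other items. What the documents demonstrate is an undefined period. This stands, and it makes the 12:3:3:6:6:6 pattern conditional.
- **No resource-use table is visible.** SAP 6.7 is a general rule. Change from baseline is specified only for vital signs, exercise tests and laboratory values. The display plan of 24 April 2020 cited in SAP 7 is not among the documents, and redacted or omitted sections could hold a relevant rule. This stands: the tables could show the pattern, but it cannot be said that they will.
- **Some items are already handled.** Protocol 9.8.1 plans incidence rates with confidence intervals for events during follow-up, and Annex 3 records hospital entry and discharge dates. Dated stays can be assigned to any period. This stands for stays and events. Physician contacts, procedures and lost work days are not clearly events, and the visible SAP text gives no rates.
- **The diagnostic work-up is real use.** Patients diagnosed less than 6 months before entry have a 12-month look-back that always spans the diagnosis. That is not an artefact, and stratification by time since diagnosis is already planned. It calls for a note, not for dropping their baseline from the trend, although 9.8.1 makes this stratum decisive when results conflict.
- **The study is descriptive.** This does not answer the point, because the descriptive trend is what would mislead.

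**Conclusion.** The point holds in conditional form. It is established that the baseline count covers 12 months, that the visit gaps are unequal, that the follow-up look-back is unstated, and that the visible SAP summarises by nominal visit without a time denominator. If follow-up counts run from the previous visit and raw counts are tabulated by visit, constant use appears as a 75% fall from baseline to months 3 and 6 and then stays at half of baseline from month 12. The ratios do not depend on the true rate of use.

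It applies mainly to physician visits, procedures, rehabilitation days and lost work days. A spread of 2 to 10 months is possible only at months 18 and 24, and a five-fold difference only at months 6, 18 and 24. A missed visit does not always double the period. This is a modest flaw that is worth correcting because it bears on a named objective and costs little.

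**What to change.** 1. Confirm what the follow-up question in the eCRF asks, and state that look-back in Table 1 (for example, the time since the last documented visit).
2. In SAP 5.1 and 7.4, put the undated counts on a common time scale. One option is use per patient-month or patient-year, with the baseline count divided by 12 months and each follow-up count divided by the actual time it covers. The other is yearly totals (M3 + M6 + M12, and M18 + M24) beside the 12-month baseline.
3. Describe trends over time only on that scale. The rate form copes better with missed visits, early leavers and off-schedule dates.
4. Add a note that the baseline figure of newly diagnosed patients can include the diagnostic work-up.

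**Cost.** One SAP paragraph, one derived variable, one Table 1 footnote and a little more analysis work. Annex 4 already attaches dates to vital signs, so new data should not be needed, but the denominator is right only once the eCRF look-back is confirmed. SAP version 2.0 is dated 13 May 2020 and data collection is planned to end on 5 June 2021, so on the documents' own dates the rule could still be fixed in advance.

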## **7.4 NATURAL COURSE**

Data on the natural course of IPF are from retrospective and a few prospective studies, including the placebo arms of clinical trials (limited to short observation periods and by in/exclusion criteria). The previously reported median survival time of 2-3 years from the time of diagnosis could be an underestimate, at least when accounting for patients with preserved lung function. Notably, the natural course is unpredictable for a given patient at the time of diagnosis, while the majority of patients experience steady worsening (slow progression), others remain stable, or have rapid progression of disease [\[10-11\]](#). Acute respiratory worsening either due to secondary complications (e.g. pneumonia, pulmonary embolism, pneumothorax or cardiac failure) or due to unknown reasons (in this case the term acute exacerbation is used) are suggested to occur in about 5-10% annually [\[1\]](#). A recent retrospective review of 461 patients with IPF has found that the 1- and 3-year incidences of acute exacerbations were 14.2% and 20.7%, respectively [\[12\]](#).

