## **7.6 ECONOMIC ASPECTS**

IPF is of high interest for the health-care system as well as for payers when considering costs. However, data on economic issues are limited, while needed for assessing cost-effectiveness of interventions [\[16-17\]](#).

The current IPF Registry will be suitable for various cost analyses. All pharmaco- and health economic parameters will be derived from either one or both of the following ways and in most cases subsequently priced:

- Assessment of the direct health resources use
- Indirect health assessment with adjustment of recorded clinical outcomes.

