### **9.3.2 Withdrawal Criteria**

The patients reserve the right to withdraw consent at any time during the study, without the need for justification and without any impact on their future treatment and care.

Withdrawal of consent means that the patient does not wish or cannot continue to participate in the study any more.

The reasons for withdrawal may include the following:

- Patient or legally accepted representative withdraws informed consent for participation in the study.
- Inclusion or possible participation in any clinical trial, any time within the follow up period of the study, in which the patient has been exposed or is going to be exposed to an investigational product (pharmaceutical product or medical device) or intervention.
- The patient was erroneously included in the registry
- Decision of the investigator/physician
- Important deviation/divergence from the protocol.

The Clinical Monitor at BI or BI's designees must be immediately notified if a patient is discontinued prematurely for any of the instances reasons cited above.

Patients that withdraw from the study should be asked about the reason(s) for withdrawal and the occurrence of adverse events, and should be examined and evaluated by the investigator according to the procedures that are defined in the Final Visit (unless reason for discontinuation is erroneous enrolment of the patient into the study at baseline and unless patient has actively withdrawn consent for any kind of future contacts).

If the patient specifically withdraws consent for future contact about the collection of further information, there will be no such contact whatsoever. However, it is possible to collect information regarding their survival status, if they are publicly available.

The investigators also reserve the right to remove a patient from the study, if according to their clinical judgment this is the necessary for the patient's welfare.

If a patient is removed or withdrawn from the study for any reason, the date, vital status and reason must be documented in the relevant section of the electronic Case Report Form (eCRF).

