- Clinical events and hospitalizations especially due to: (acute) respiratory worsening, including pneumonia, exacerbations of IPF, occurrence of pulmonary or cardiovascular complications, pulmonary rehabilitation, pulmonary embolism, pneumothorax, or cardiac failure
- Management of IPF and physician contacts

During follow up visits (prospectively until up to 2 years at least from the inclusion) 3-months (+/- 1 month), 6-months (+/- 1 month), 12-months (+/- 2 month), 18-months (+/- 2 month) and 24 months (+/- 2 months), documentation of events (or last follow up visit) will be carried out. The collection of data will be performed during standard clinical practice visits (i.e. visits should not be performed via telephone contact). In a special event where the physical presence of the patient is not possible, e.g. in case of temporary inability of the patient to visit the expert center, this visit could be performed through telephone contact and this should be recorded in patient's history. Every effort should be made, however, to ensure that the next visit will be performed as planned by the patient in person. If this is not possible the patient will be censored for the rest of the study. Patient will be followed up until death, lung transplantation, consent withdrawal or end of study, whichever comes first and will be censored if one of the events occurs. The following data will be documented:

- Clinical course of IPF (e.g. regarding symptoms, lung functionality, exercise ability, if available)
- Vital status
- Physical and vital signs examination
- Cardiopulmonary exercise testing (6-minute walk distance and CPET, if performed)
- Autoimmune Biomarker results (No additional specimen will be collected. Only already existing data will be used from exams that have been performed according to the routine clinical practice of the physicians)
- Risk of bleeding and thrombosis
- Outcomes of interest (such as acute respiratory worsening, exacerbations, hospitalization due to any cause and due to IPF). Please, refer to [Annex 3](#)
- Recording of therapeutic algorithms (change/complement/interrupt treatment) and non-pharmacological treatment (e.g. start of LTOT, new listing for lung transplantation)
- Physician's clinical rating of the probable course of IPF (stable, slow or rapid

progression)

- Assessment of treatment intensity, frequencies and resource use for pharmacoeconomic analyses for the treatments described under 11.3

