## **5. ENDPOINTS(S)**

### **5.1 PRIMARY ENDPOINT(S)**

The main objective of this IPF registry is to gain further knowledge on the characteristics, management, progression and outcomes of patients with IPF as treated under real-world, clinical practice conditions in Greece.

More specifically, this registry is going to:

- Provide a comprehensive clinical picture for IPF
- Track access to health care and cost of caring for IPF patients over time
- Examine the implementation of treatment guidelines, used on patients diagnosed with IPF, according to the existing diagnosis guidelines
- Characterize patients on different treatments.

Endpoints are targeting the description of the following:

- Demographic data including age, gender and race, employment status and insurance status.
- Change from baseline in vital signs as measured at 3,6,12,18 and 24 months following to the baseline visit.
- Vital Status.
- Cardiopulmonary exercise testing (6-minute walk distance and CPET, if performed)
- Change from baseline in 6-minute walk distance VO2max (CPET) as measured at 3,6,12,18 and 24 months following to the baseline visit.
- IPF risk factors as measured at baseline visit: (cigarette smoking including pack years, alcohol and substance abuse, environmental and occupational exposure, exposure to drugs associated with IPF, exposure to viral infection possibly related to IPF, gastro - oesophageal reflux, genetic factors - family history).
- Description of the comorbidities throughout the trial.
- Risk of bleeding and thrombosis as stated in the CRF.
- Description of the newly diagnosed patients of acute respiratory worsening, exacerbations, and hospitalization due to any cause and due to IPF.
- Description of the intensity of treatment, frequencies and resource utilization for pharmaco-economic analyses.
- Description of methods and procedures used in the diagnosis of IPF and time since diagnosis.
- Description of IPF symptoms (dyspnea, cough, weight loss, fatigue, dizziness, chest pain, anxiety, clubbing, bibasilar crackles)

- Description of autoimmune biomarker.
- Description of lung function and/or exercise capacity.
- Description of IPF treatment modalities.
- Description of Physician's clinical rating of the probable course of IPF (stable, slow or rapid progression).

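### Physician-contact, procedure, rehabilitation and lost-work counts are taken only at scheduled visits, so in patients who die those counts from the last visit to death are likely to be lost

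*Protocol*

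**What the plan says.** Cost of care is among the registry's stated aims: SAP 5.1, like protocol sections 8 and 9.4.3, includes the item "Track access to health care and cost of caring for IPF patients over time". SAP 5.1 also lists resource utilisation among the primary endpoints. Protocol section 7.6 explains where costs come from: "All pharmaco- and health economic parameters will be derived from either one or both of the following ways and in most cases subsequently priced". One way is direct resource use; the other is indirect, through recorded clinical outcomes.

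The collection schedule is "Table 1. List of variables to be documented (if available) at scheduled visits". Its count-type rows include "Number of physician visits (own office, other physicians"), the number and type of IPF-related procedures, and "Number of days in hospital or in rehabilitation; work days lost due to IPF". Each is marked at baseline, with a 12-month look-back, and at follow-up, with no look-back stated. Follow-up means months 3, 6, 12, 18 and 24.

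On the end of follow-up, section 9.4 states: "Patient will be followed up until death, lung transplantation, consent withdrawal or end of study, whichever comes first". A closing assessment is described for patients who withdraw, who "should be examined and evaluated by the investigator according to the procedures that are defined in the Final Visit". Nothing equivalent is described for death. Annex 3 asks for its date and cause.

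Other items are dated. Annex 3 records entry and discharge for each hospitalisation, with ventilation and ICU. Annex 4 adds emergency-room and ambulance use and lets the stay end on the date of death. Section 9.4.4 asks for start and stop dates of the listed treatments.

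In the SAP, section 6.6 imputes nothing and summarises only available data. Section 6.7 analyses by nominal CRF visit and does not count unscheduled visits for the primary and secondary endpoints. No costing method or cost denominator is given.

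**The concern.** A count taken at a visit can only describe the time before that visit. A patient seen at month 6 who dies at month 10 has no month-12 visit at which the last four months of physician contacts, procedures, rehabilitation days and lost work days would be entered. The plan names nobody to enter them and no form on which to do so. An unscheduled visit in those months would not help, because SAP 6.7 keeps it out of the endpoint summaries.

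The loss falls only on patients whose follow-up ends between visits, and mainly on those who die. It cannot be repaired at analysis if the counts were never collected. What is at stake is the completeness of the outpatient and procedure part of resource use, and of any cost total built on it.

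**Working it through.** **The plan's own figures.** The documents give no figure for resource use, cost or deaths between visits. The one computed table on study size (Table 2, precision of a proportion) reproduces to rounding but does not bear on this point. The size of the gap therefore has to be derived.

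**Inputs**
- Visits at months 0, 3, 6, 12, 18 and 24 (Table 1 footnote).
- About 300 patients (protocol 9.6).
- Median survival of 2 to 3 years from diagnosis. Section 7.4 adds: "The previously reported median survival time of 2-3 years from the time of diagnosis could be an underestimate". I therefore also use 5 years, which is my assumption.
- Assumptions: exponential survival from enrolment; every visit attended on its nominal date; no withdrawal or transplantation.

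**Formulas.** With median m in months, λ = ln 2 / m and S(t) = exp(−λt).
- Deaths by month 24: 300 × (1 − S(24)).
- Person-time to month 24 per patient: T = (1 − S(24)) / λ.
- Time from last visit to death, for an interval from a to b with w = b − a: S(a) × [(1 − exp(−λw))/λ − w × exp(−λw)]. Summing over the five intervals gives L.

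**Worked case, m = 24.** λ = 0.02888 and S(24) = 0.5, so T = 0.5 / 0.02888 = 17.31 months.
- For months 6 to 12, S(6) = 0.8409 and exp(−6λ) = 0.8409. The term is 0.8409 × (5.509 − 5.045) = 0.390.
- The five terms are 0.123, 0.113, 0.390, 0.328 and 0.276, so L = 1.23 months per patient.
- L / T = 1.228 / 17.31 = 7.1%.
- Mean gap per death: 1.228 / 0.5 = 2.5 months.

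| Median survival | Deaths by month 24, of 300 | Mean gap per death (months) | T (months) | L (months) | L / T |
|---|---|---|---|---|---|
| 2 years | 150 | 2.5 | 17.31 | 1.23 | 7.1% |
| 3 years | 111 | 2.5 | 19.22 | 0.93 | 4.8% |
| 5 years (assumed) | 73 | 2.6 | 20.96 | 0.62 | 3.0% |

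**From lost time to lost use.** Let use in the gap be k times use at other times. The share of the total that is missed is kL / (T − L + kL). If person-time also stops at the last visit, the observed rate divided by the true rate is T / (T − L + kL). The documents give no value for k, so the rows other than k = 1 are illustrations only.

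| k | Total understated (median 2 / 3 / 5 years) | Rate per observed month |
|---|---|---|
| 0.5 | 3.7 / 2.5 / 1.5% | too high by 3.7 / 2.5 / 1.5% |
| 1 | 7.1 / 4.8 / 3.0% | unbiased |
| 2 | 13.3 / 9.2 / 5.7% | too low by 6.6 / 4.6 / 2.9% |

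If the denominator ran to death while the counts stopped at the last visit, the rate would be understated by the same percentage as the total. Neither document says which denominator applies.

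**The case against.** The strongest reply is that much of the health-care use before death can be recorded without a later visit. This stands for admissions and drugs. Annexes 3 and 4 give entry and discharge-or-death dates together with ICU, ventilation, emergency-room and ambulance use, so hospital days follow from the dates even though they share a Table 1 row with rehabilitation and lost work days. Treatment dates and a dated death give drug exposure up to death. Section 7.6 also allows costs to be derived indirectly from clinical outcomes.

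A second reply is that section 9.5 has data collected as events happen, and that sections 9.5 and 9.7 draw on medical records. This stands only in part. The same sentence of section 9.5 ties collection to the approximate visit schedule, and access to records shows that the counts could be retrieved, not that anyone is asked to retrieve them. Section 9.3.3 allows unscheduled visits when events occur, but SAP 6.7 keeps them out of the endpoints.

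A third reply is that the eCRF, the data management plan and the display plan are not available here, so a death page with resource items may exist. That is possible. The protocol and SAP do not mention one.

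A reader might go further and infer that nothing is recorded before death, or that the overall cost of care is understated by a large and certain amount. The documents support neither. Admissions and drugs are dated, and a large figure needs a steep rise in use before death that the documents do not quantify. Such a rise is more plausible for admissions than for clinic contacts, rehabilitation or work days, which could even fall in a patient who is in hospital or retired.

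**Conclusion.** The point holds for the count-type items only: physician visits, IPF-related procedures, rehabilitation days and lost work days. Followed as written, the plan leaves these uncollected from the last scheduled visit to death, and totals for them are likely understated.

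At constant use, and if nothing in the interval is otherwise captured, the understatement is 4.8 to 7.1% at the protocol's survival figure and 3.0% at the assumed 5-year median. It is larger only if outpatient use rises before death. A rate per observed month is unbiased at constant use, so downward bias in a rate is not established.

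The main weakness of the sizing is the survival input. The protocol's median runs from diagnosis, whereas the registry also enrols previously diagnosed patients, who may be more stable according to section 9.10. Withdrawal, transplantation and missed visits are left out. This is a modest loss, but it is confined to patients whose follow-up ends early, affects a stated objective and is avoidable.

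**What to change.** **Protocol 9.4 and Table 1.** When a patient dies or is transplanted, the site completes the count items from the medical file, for the time from the last visit to that date, on the end-of-follow-up page. State that follow-up counts cover the time since the last visit.

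**SAP 6.7 and 7.4.** Exempt resource use from the exclusion of unscheduled visits. Count the final interval in both the numerator and the person-time, and say which denominator any rate or cost summary uses.

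**Cost.** One short page per death or transplantation, filled from records the centre holds, plus the SAP wording. Contacts outside the centre may be incompletely known, so the report should state that the final interval rests on the centre's own records.
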